Aim R3: Stage 2: Implement an RCT to test the main hypothesis that the use of personalized decision aids leads to (i) an increase in the proportion of women who would consider active surveillance as a viable management strategy for DCIS, and (ii) an increase in knowledge of the associated risk trade-offs.

C. Research Questions

Primary

[figure not shown]
Compared to presenting active monitoring (AM) as an experimental option, does presenting AM as a guideline-concordant care option increase its uptake as treatment choice?

Secondary

Compared to presenting active monitoring (AM) as an experimental option, does presenting active monitoring as a guideline-concordant care option increase AM acceptability, decrease perceived AM riskiness, and decrease uptake of mastectomy as treatment choice?

D. Study Design

Two-arm parallel randomized controlled clinical trial stratified by age (<65 vs. ≥ 65). Block-randomized in both age strata, with block sizes of n=6.

Control: Decision tool with AM:

- AM portrayed as experimental approach currently evaluated in clinical trials
- Contains in-depth information about the 3 surgical options only

Intervention: Decision tool with AM:

- AM offered as standard of care alongside lumpectomy, lumpectomy with radiation, and mastectomy
- Contains in-depth information about all 4 options

Primary data collection with healthy trial participants. All measures, except for participant age, are self-reported. Participants complete a baseline survey prior to randomization (Decision tool with or without AM), use the Decision tool, and then complete a post survey immediately after. The entire session is expected to take less than 1 hour to complete.

E. Sample Size & Randomization

Prior information

- COMET study team poll (n=4): Intervention uptake of AM estimated to be ~15%
- Patient advocate poll (n=10): Intervention uptake of AM estimated to be ~35%

- Currently, <3% of patients do not undergo surgery after diagnosis with DCIS (any type of DCIS)
- Usability testing (much closer to intervention than control version, n=19): uptake ~40%

Targets

- Assume control arm has AM uptake of ~5%
- Difference intervention vs control is thus ~10% (COMET study team) to ~30% (patient advocates)
- Clinically meaningful difference is ~15%
- We want to calculate sample size for $\Delta=15\%$ (control at 5%, intervention at 20%) at significance level $\alpha = 0.05$ and $\geq 90\%$ power

Calculations:

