- Used Mantel-Haenzel test (note: Table below created with power.prop.test in R)
- Scenario 1: we have 90% power with n=101 in each arm
- Scenario 2: if Δ is still 15% but control/intervention at 10%/25% we still have 80% power
- Scenarios 3-6: if, as estimated in usability testing, uptake of AM is 40%, then for Δ of 15%, 20%, 25% and 30%, we have power of 62%, 88%, 98% and 99%

Scenario	n (per arm)	P1	P2	Δ	Power
1	101	5%	20%	15%	90%
2	101	10%	25%	15%	80%
3	101	10%	40%	30%	99%
4	101	15%	40%	25%	98%
5	101	20%	40%	20%	88%
6	101	25%	40%	15%	62%

Randomization

- We prepare two separate random streams, one for younger (<65 years) and one for older (≥ 65 years) participant strata.
- Each stream is block randomized, with block size $k=6$.
- For each consented participant, we check for survey completion. Survey completion is defined as:
 - Reached the end of the survey (and thus were paid); and
 - Answered the treatment choice question (primary outcome); and
 - Answered the treatment acceptability questions (n=4; secondary outcome); and
 - Answered perceived riskiness question (secondary outcome); and
 - Answered both pre- and post-tool self-reported knowledge questions about DCIS (secondary outcome); and
 - Clicked on the Guide and the Decision Support Tool links provided in the survey.
- We continue to randomize until we reach n=101 participants (per arm) who pass the survey completion check.

F. Study Sample

Potential patients will be identified through Duke electronic health record system Epic and invited through the MyChart patient portal. Duke has an “opt-out” system that allows patients to be contacted directly about research studies for which they may be eligible. If a patient agrees to participate in the study by replying to a MyChart message, the patient will be consented and referred to the survey link.

Inclusion criteria

- Female
- Age 50-79

- No history of DCIS/breast cancer [medical record only]
- Negative mammogram in past 12 months [medical record only]

G. Outcomes & Hypotheses

Primary Outcome: Post-tool choice of active monitoring (AM). Presented to participants as a categorical item: active monitoring, lumpectomy, lumpectomy with radiation, mastectomy. Recorded for analysis as binary: AM vs non-AM.

Q1: If you were a patient diagnosed with DCIS, what treatment option would you choose?

[Order is randomized]

- Active monitoring
- Lumpectomy
- Lumpectomy with radiation
- Mastectomy

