To answer the primary research question, we will use a log-binomial regression model to test the effect of study arm on binary treatment choice (see primary outcome measure), controlling for age group to account for the stratified design:

$$(1) \quad Y_i = \beta_0 + \beta_1 X_i + \beta_2 a_i$$

where

Y_i = subject i 's response: $Y=1$ for AM, $Y=0$ for non-AM choice

X_i = subject i 's study arm: $X=0$ for control arm, $X=1$ for intervention arm

a_i = subject i 's age group: $a=0$ for age <65 years, $a=1$ for age ≥ 65 years

The main effect of interest (1) is represented by β_1 which quantifies the difference in AM uptake between the two arms and will be reported as $\exp(\beta_1)$ with 95% confidence interval [CI].

To follow the CONSORT statement and because the control arm prevalence is expected to be $>10\%$ we will report risk ratios as the relative measure, and absolute risks in both arms.

K.3. Secondary outcome analyses

Secondary Outcome 1. Linear regression model, as in (1), reported as β_1 (95% CI).

Secondary Outcome 2. Linear regression model, as in (1), reported as β_1 (95% CI).

Secondary Outcome 3. Same analysis as primary outcome analysis, reported as β_1 (95% CI).

Secondary Outcome 4. Linear regression model, controlling for age group, and with random intercepts to account for within-subject dependence.

Model:

$$(1) \quad Y_{ij} = \beta_0 + \beta_1 X_i + \beta_2 t_j + \beta_3 t_j X_i + \beta_4 a_i$$

where

Y_{ij} = subject i 's response at time t_j . (0=surgical; 1=AM)

t_j = time (0=pre-tool; 1=post-tool)

X_i = subject i 's study arm (0 = control; 1 = intervention)

a_i = subject i 's age group: $a=0$ for age <65 years, $a=1$ for age ≥ 65 years

If the models for secondary outcomes 1-4 do not meet the required assumptions for linear models, we will explore using median regression and/or dichotomizing the continuous variable (e.g., top quartile=high, remaining values=normal/low).

K.4. Exploratory aims analyses

Ad hoc statistical analyses will be performed for exploratory aims 1-4. For Exploratory Aim 5 (association of covariates and additional scales with choice), we will extend the model (1) to include covariates and additional scales as outlined sections I and J above. The additional model features will first be assessed for multicollinearity, with features removed if necessary. We will do model building to identify a final model, and present both unadjusted and adjusted parameter estimates for the final model (Table 3).

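### SAP Section E sizes the trial on about 5% control uptake of active monitoring while K.2 expects more than 10%; on K.2's figure, planned power for the 15-point target is at most about 80–82%, not 90%

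*SAP*

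**What the plan says.** SAP Section E, Targets, states "Assume control arm has AM uptake of ~5" per cent. Two further statements depend on that figure.

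- **Expected differences:** "Difference intervention vs control is thus ~10% (COMET study team) to ~30% (patient advocates"). These are the two polls' intervention estimates minus 5 points. The first poll, for example, reads "COMET study team poll (n=4): Intervention uptake of AM estimated to be ~15" per cent.
- **Sizing case:** "We want to calculate sample size for" a 15-point difference, control 5% and intervention 20%, at alpha 0.05 with power of at least 90%. The 15 points come from the bullet "Clinically meaningful difference is ~15" per cent.

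Under Calculations, the sizing case becomes "Scenario 1: we have 90% power with n=101 in each arm". The next line keeps 15 points but raises the control rate: "control/intervention at 10%/25% we still have 80% power". Scenarios 3–6 fix intervention uptake at 40% with control at 10%, 15%, 20% and 25%, giving 99%, 98%, 88% and 62%.

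K.2 of the same SAP version gives two reasons for reporting risk ratios. One is CONSORT. The other is "because the control arm prevalence is expected to be" above 10%.

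The Protocol (Research Design), which is later than the SAP, fixes 202 women and gives no control rate.

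**The concern.** A control rate of about 5% cannot also be above 10%. Both statements concern the primary outcome in the same arm, both are current text, and no passage explains the difference.

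The 5% figure matters because power for a fixed absolute difference falls as the control rate rises towards 50%. A reader of Section E takes 90% as the planning power for the difference the SAP calls clinically meaningful. A reader of K.2 learns that the investigators expected a control rate at which the SAP's own table gives 80% or less for that difference.

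What is at stake is how a null result would be read. At 5%/20% the chance of missing a true 15-point difference is about 8–10%, depending on the test. At 10%/25% it is about 18–20%, and it grows above that. The SAP does not say which of these was planned for.

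**Working it through.** **Inputs.** 101 per arm, alpha 0.05, 15-point difference, control 5% (Section E) or above 10% (K.2). Allocation is 1:1 (Protocol, Research Design). Sidedness is not stated. Two-sided is inferred because it reproduces all six table rows, whereas one-sided would give 94.7% for Scenario 1 and 88.2% for Scenario 2. There is no dropout inflation, because randomisation continues until each arm has 101 women who pass the completion check.

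**Formula** (R's power.prop.test, which the SAP says produced its table). With p̄ = (p1 + p2)/2 and Δ = p2 − p1:

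power = Φ{ [√n·Δ − 1.960·√(2p̄(1−p̄))] / √(p1(1−p1) + p2(1−p2)) }

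**Step 1: reproduce the SAP's 90%.** At 5%/20%, p̄ = 0.125, √(2p̄(1−p̄)) = 0.4677, and the denominator is √(0.0475 + 0.16) = 0.4555. The numerator is 10.050 × 0.15 − 1.960 × 0.4677 = 1.5075 − 0.9167 = 0.5908. Then 0.5908/0.4555 = 1.297 and Φ(1.297) = 90.3%. Scenarios 2–6 give 80.6, 99.9, 98.2, 87.9 and 62.6%, against 80, 99, 98, 88 and 62 printed. All agree to rounding or truncation.

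**Step 2: the same target at the edge of K.2's range.** At 10%/25%, p̄ = 0.175, √(2p̄(1−p̄)) = 0.5374, and the denominator is √(0.09 + 0.1875) = 0.5268. Then (1.5075 − 1.0532)/0.5268 = 0.862 and Φ(0.862) = 80.6%.

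**Step 3: other control rates and other tests.** The SAP names a Mantel-Haenszel test for sizing and a log-binomial model for analysis, so the result was checked beyond the approximation. All entries are power for 15 points with 101 per arm, two-sided.

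| Control / intervention | power.prop.test | Exact chi-square | Mantel-Haenszel (simulated) | Wald test on log risk ratio |
|---|---|---|---|---|
| 5% / 20% | 90.3% | 92.4% | 92.4% | 90.6% |
| 10% / 25% | 80.6% | 82.0% | 81.7% | 80.1% |
| 11% / 26% | 78.8% | 80.2% | – | 78.2% |
| 15% / 30% | 72.7% | 73.4% | 73.1% | 71.9% |
| 25% / 40% | 62.6% | 62.5% | 62.6% | 61.2% |

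The simulation used 400,000 trials, no continuity correction, a 51/50 split of each arm by age and equal uptake in both strata. A 71/30 split moves results by under 0.2 points. The chi-square and Wald columns ignore the age strata. Rates above 10% are illustrative, because K.2 gives only a lower bound; 15% and 25% are control rates in the SAP's own table.

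**Step 4: what 90% power would cover at 10% control.** By the Step 1 formula, 101 per arm gives 90% power for a difference of 17.65 points, about 18. For 15 points, n = [(1.960 × 0.5374 + 1.282 × 0.5268)/0.15]² = 132.8, so 133 per arm. That is 266 in total, 64 more than 202.

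**Step 5: the poll-based differences.** At 10% control they become 15 − 10 = 5 points and 35 − 10 = 25 points, in place of the stated 10 and 30, and smaller still above 10%.

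**The case against.** The strongest reply is that the SAP already discloses the consequence. Scenario 2 prints 80% next to the 90%, Scenario 6 prints 62%, and five of the six scenarios have control uptake of 10% or more. This stands: nothing was hidden and the table needs no correction. But those rows are offered as alternatives to the sizing case. Showing a sensitivity case does not say which case is expected, and the bullet of expected differences still subtracts 5%.

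A second reply is that K.2's clause does no sizing work. It supports a reporting choice that CONSORT supports by itself, and it gives a bound without a source. This also stands, and it is why deleting the clause is an acceptable repair. It does not remove the contradiction.

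Third, the interpretive harm is limited. K.2 reports the risk ratio with its 95% confidence interval and the absolute risks in both arms, so a null result can be judged from the interval and the observed control rate. That is correct, and it keeps this a matter of consistency in the plan.

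A reader might go further and infer that the trial is underpowered, or that it must grow to 266. The documents do not support that. The shortfall is confined to differences near 15 points. With intervention uptake at 40%, as in usability testing, and control at 10–20%, Scenarios 3–5 give 99%, 98% and 88%. Nor do the documents show which of the two control rates is right.

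**Conclusion.** The inconsistency is real and should be corrected. Section E's 90% is right for 5% against 20%. If control uptake exceeds 10%, as K.2 expects, power for 15 points with 101 per arm is at most about 80–82%: 80.6% by power.prop.test and 82.0% by exact chi-square at 10% control. It falls to about 73% at an illustrative 15% and about 62% at the SAP's own 25%. Two Targets statements then fail: at least 90% power for 15 points, and the poll-based differences of 10 to 30 points.

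The result assumes a two-sided 5% test and equal arms of 101; the Mantel-Haenszel check also assumes equal uptake in the two age strata. The choice of test moves the figure at 10% control by about 2 points and does not alter the conclusion. No arithmetic error is claimed, and no estimate, test or enrolment number is affected.

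**What to change.** Use one control-rate expectation in Section E and K.2, and keep n=202. The choice should rest on what was expected at planning, not on accrued outcome data.

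**(A) If above 10% stands, revise Section E:**

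1. Replace the 5% bullet with: *Control-arm AM uptake is expected to exceed 10% (see K.2).*
2. Replace the bullet that seeks at least 90% power with: *The size of 101 per arm was derived for 5% versus 20%. At 10% control it gives about 80% power for 15 points, and less at higher control rates; 90% power at 10% control applies to about 18 points.*
3. Label Scenario 1 as the original sizing case, not the expected case. Scenarios 2–6 stay as printed.
4. Delete the bullet of poll-based differences, or recompute it as about 5 to 25 points at 10% control and less above that.

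**(B) If about 5% stands,** delete the clause in K.2 that expects more than 10% and rely on the CONSORT reason for risk ratios.

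Option A costs three reworded bullets, one label and a lower stated power for 15 points. Option B costs one deleted clause. Neither changes enrolment, the primary test or the model.

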Finally, we will perform exploratory attrition analyses. First, we will compare the number of participants who expressed interest, consented, started the experiment, finished the experiment, and were included in final analysis. Second, if there are 20 or more participants who started the experiment but did not finish it, we will compare any completed baseline items

K.5. Missing Data

During data checks, we will determine the degree to which variables of interest are going unanswered. Depending on the type of variable and the amount of missingness across all subjects, as well as the balance across study arms, we will consider different imputation methods, or removal of the covariate from the models. For variables with a low degree of missing values (<=5%), we will use simple imputation methods, substituting in the median or modal response. For variables with a higher degree of missing values (>5%) we may perform multiple imputation with 25 imputations.

K.6. Subgroup Analysis

Stratification by age group (<65 vs. \geq 65 years) will occur during study arm assignment to ensure equal age group representation in each study arm. Further, we plan to analyze the effect of study arm on treatment choice separately within each of the two major age groups, while still including age in years as a continuous covariate. If there is a very marked difference in the stratified analysis, we could consider only including the stratified analysis (i.e. if the overall model is a poor indication of treatment effects because of the subgroup differences).

K.7 Sensitivity Analyses

Intent-to-treat vs. per Protocol analysis: Run both Table 1 and primary outcome model for the final sample with all exclusion criteria applied, as well as for the larger sample of all participants who were randomized and completed the post-survey. This comparison will only be necessary if >5% of those randomized, who completed the post-survey, were excluded due to not clicking through the guide and tool (new criteria).

Anticipated tables and figures

Table 1. Participant characteristics (demographic, pre-knowledge), overall and by treatment arm

Table 2. Primary and secondary outcomes at each time point, and change, by treatment arm

Table 3. Intervention effects on primary outcome

Figure 1: Proportion of treatment choice selections post-tool by study arm (*format TBD*)

Table 1. Patient characteristics, overall and by arm (demographics by age group included as a supplemental table)

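### The SAP names no primary analysis set, and Sections E and K.7 imply one that drops randomised women whose treatment choice was recorded but who later failed the completion check

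*SAP*

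**What the plan says.** SAP K.2 states that "we will use a log-binomial regression model to test the effect of study arm on binary treatment choice", with age group as covariate. It does not say which randomised women are analysed.

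SAP E sets the accrual rule: "We continue to randomize until we reach n=101 participants (per arm) who pass the survey completion check". To pass, a woman must answer the treatment-choice item, the four acceptability items, the perceived-risk item and the pre- and post-tool DCIS knowledge items. Two further criteria matter most here:

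- "Reached the end of the survey (and thus were paid); and"
- "Clicked on the Guide and the Decision Support Tool links provided in the survey"

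SAP K.7 compares two samples. One is described so: "Run both Table 1 and primary outcome model for the final sample with all exclusion criteria applied". The other, under the intent-to-treat label, is "the larger sample of all participants who were randomized and completed the post-survey". The comparison is conditional: "This comparison will only be necessary if >5% of those randomized, who completed the post-survey, were excluded due to not clicking". The clicks meant are those on the two links named in E.

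SAP K.4 plans to count women at each stage, listing those who finished separately from those in the final analysis. It adds an attrition check: "if there are 20 or more participants who started the experiment but did not finish it, we will compare any completed baseline items". SAP K.5 deals with unanswered variables and imputation.

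In Protocol Appendix 1 the treatment-choice item falls between the 18% and 21% markers. The last secondary item in the check comes before the 33% marker. Knowledge, decision-preparation, literacy, personality and demographic items follow.

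**The concern.** Section E on its own is a recruitment rule. Read with K.7, it becomes the working definition of the primary sample, and that sample is selected after randomisation. Under SAP D only the pre-tool knowledge item comes before randomisation; under the Protocol's phase order (Research Design) none of the criteria does. Most are met after the woman has seen content that differs by arm: in-depth information on four options in one, on three surgical options in the other.

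Stopping part-way or leaving items blank could therefore be related to both the arm and the choice made. If it is, the primary RR no longer compares the groups as randomised, although the missing outcomes may already have been recorded. Failure to click a link is the lesser worry, because it is less a reaction to the content. The Guide link, for instance, is clicked before any content is seen.

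**Working it through.** **1. The plan's own figure.** Inputs from SAP E: 101 per arm, 5% vs 20%, α = 0.05 (taken as two-sided). With pooled variance and no continuity correction:

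z = (0.15·√101 − 1.96·√(2·0.125·0.875)) / √(0.05·0.95 + 0.20·0.80) = (1.507 − 0.917)/0.456 = 1.30

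This gives power of 90.3%, against 90% stated. The sample size is not in dispute.

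**2. A woman who answers every item in the check, then stops after the 33% marker.**

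| Section | What happens to her |
|---|---|
| E | Did not reach the end; fails; randomisation continues until others fill the 101 |
| K.2 | No analysis set, so no instruction to include her |
| K.7, main sample | Excluded |
| K.7, wider sample | Excluded if completing the post-survey means reaching its end (the natural reading; not defined) |
| K.4 | Counted; baseline items compared if 20 or more did not finish; no outcome model |
| K.5 | Covers unanswered variables; does not say excluded women return |

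**3. The K.7 trigger.** With 202 women passing and E finishers excluded only for not clicking, the share is E/(202 + E).

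- E = 10: 10/212 = 4.7%, comparison not required.
- E = 11: 11/213 = 5.2%, comparison required.

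Early stoppers do not enter this ratio on the natural reading, however many there are.

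**4. Size of bias under assumed failure rates.** The documents give no rate, so these are assumptions. Let p be true uptake of active monitoring (AM) in an arm, a the failure rate among AM choosers and b that among the rest. Uptake among women who pass is

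p(1 − a) / [p(1 − a) + (1 − p)(1 − b)]

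| Who fails | Intervention uptake observed | True RR | RR observed |
|---|---|---|---|
| 10% of intervention non-AM | 0.20/(0.20 + 0.72) = 0.2174 | 4.0 (5% vs 20%) | 0.2174/0.05 = 4.35 |
| 10% of intervention AM | 0.18/(0.18 + 0.80) = 0.1837 | 4.0 | 0.1837/0.05 = 3.67 |
| 10% of every group | 0.18/(0.18 + 0.72) = 0.20 | 4.0 | 0.20/0.05 = 4.00 |
| 10% of intervention non-AM | 0.2174 | 1.0 (20% in both) | 0.2174/0.20 = 1.09 |
| 20% of intervention non-AM | 0.20/(0.20 + 0.64) = 0.2381 | 1.0 | 0.2381/0.20 = 1.19 |
| 20% of intervention AM | 0.16/(0.16 + 0.80) = 0.1667 | 1.0 | 0.1667/0.20 = 0.83 |

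In the 1.09 and 1.19 rows the two-sided rejection rate under no effect is about 6.1% and 10.0%, against 5%. For scale, losing 10% of non-AM choosers at 20% uptake removes 8% of the arm: about 101/0.92 = 110 intervention women with a recorded choice, of whom 9 are dropped.

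If failure depends on choice alone, equally in both arms, the null stays at 1. A true 4.0 hardly moves: with 10% of non-AM choosers lost in both arms, 0.2174/[0.05/(0.05 + 0.855)] = 0.2174/0.0552 = 3.93.

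**5. Power after the change.** If a fraction d of women with a recorded choice fail the check, n per arm is 101/(1 − d). For d = 2%, 5%, 10% and 20% this is 104, 107, 113 and 127, with power of 91.1%, 91.8%, 93.2% and 95.5% at 5% vs 20%.

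**The case against.** The strongest reply is that losses will be few and harmless. The task is a single session expected to take less than an hour, payment depends on finishing, and nothing in the documents shows that stopping would depend on arm and choice together. This stands as a limit on size. It does not supply an analysis set, and if losses are few, including these women costs little.

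A second reply is that E governs accrual only. That is right: the primary set is inferred. But K.7's wording makes the inference strong, and no section points to another set.

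Third, K.7 already offers a wider sample, and its trigger does not forbid running it below 5%. K.4 also plans part of the participant flow. Both are true. K.7 would bring back finishers who did not click and, on one reading, finishers who skipped an item.

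Three stronger readings are tempting and not supported:

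- A reader might infer that ten excluded women could overturn the result. In Scenario 1, restoring ten control women who all chose AM moves the RR from 4.00 to (20/101)/(15/111) = 1.47. But ten is the click-trigger count, and no document ties it to women who stopped. If failure were unrelated to arm and choice, that pattern would have probability (0.5 × 0.05)^10, about 10^−16.
- A reader might infer that the plan can never restore early stoppers. That depends on how completing the post-survey is meant, which the SAP leaves undefined.
- A reader might infer that the K.2 age term would be missing for early stoppers. The documents show only an ambiguity: SAP D exempts age from self-report, I.1 says self-reported age in years is used for analysis, and K.2 uses the stratification groups.

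**Conclusion.** The point holds as a gap with a cheap remedy, not as evidence that the result will be biased. K.2 names no analysis set, and following E and K.7 as written would exclude randomised women with an observed primary outcome. On the natural reading of K.7, no planned analysis includes those who chose and then stopped.

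Size and direction of any bias are unknown. Material bias requires failing the check to depend on both arm and choice. Under the assumed one-sided losses of 10%, an RR of 4.0 becomes 4.35 or 3.67 depending on who is lost, and a null RR at 20% uptake becomes 1.09 when non-choosers are lost. Equal loss in all groups changes nothing. The conclusion rests on the inferred primary set and on reading K.7's completion wording as reaching the end of the survey. It should be fixed; confidence is moderate.

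**What to change.** - In K.2, define the primary analysis as every randomised woman with a recorded treatment choice, in her assigned arm, regardless of clicks, later completion or missing secondary items.
- In K.7, always report the check-passing set as the per-protocol sensitivity analysis, and delete the 5% trigger.
- Report by arm the numbers randomised and the numbers failing each criterion.
- Take the K.2 age-group term from the stratification record. This settles the disagreement between D and I.1. Self-reported age is asked near the end of the survey and could be missing for early stoppers.
- Optionally, add best- and worst-case bounds for randomised women with no recorded choice.

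The cost is SAP wording and one extra model run. Recruitment to 101 check-passing women per arm can continue, and power does not fall under the rates in working step 5. The drawback is slight dilution from women who did not open the tool. The change assumes that answers submitted by non-finishers are kept. K.4 mentions only their baseline items, so the sponsor should confirm this for the post-tool choice.
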